2.6.2 Duration of exposure

Duration of exposure to study treatment is considered by taking into account the duration of exposure to the investigational drug:

Duration of exposure (weeks) = [(last date of exposure to study treatment) - (date of first administration of study treatment) + 1]/7,

The last date of exposure to study treatment is the date when the last study drug will be administered (see [section 2.1.2.3](#)).

Summary of duration of exposure of study treatment in weeks will include categorical summaries and descriptive summaries (i.e. n, mean, standard deviation, median, max and min) in weeks. The time interval will be categorized as: <4 weeks, 4 to <12 weeks, 12-<20 weeks 20-<=24 weeks, >24 weeks. Frequency counts and percentages will be presented for the number of patients in each time interval using the Safety Set.

2.6.3 Planned and actual dose intensity

Planned dose intensity (PDI) and actual **dose intensity** (DI) for subjects with non-zero duration of exposure are defined as follows:

PDI (mg/kg/day) = [planned cumulative dose during the time of exposure (mg/kg)]/Duration of exposure (days)

DI (mg/kg/day) = [actual cumulative dose during the time of exposure (mg/kg)]/Duration of exposure (days)

Relative dose intensity (RDI) is defined as follows:

$$\text{RDI (\%)} = (\text{DI (mg/kg/day)} / \text{PDI (mg/kg/day)}) * 100$$

Planned dose intensity, actual dose intensity and relative dose intensity (<70%, 70%-90% and >90%) will be summarized by means of descriptive statistics using Safety Set.

2.6.4 Dose Change

‘Dose interrupted’, and ‘Dose change’ fields from the Dosage Administration CRF pages will be used to determine the dose reductions, dose interruptions. The corresponding fields ‘Reason for dose changed/dose interrupted’ will be used to summarize the reasons. Dose interruption and dose reduction are defined as follows:

- **Interruption** is defined as any period of zero actual daily dose prior to treatment end date.
- **Reduction** is a subset of the dose changes, defined as a decrease from the previous planned non-zero dose, even if this decrease has been directly preceded by an interruption. Patient has dose decrease or reduction at visit if the dose assignment at the visit will be nonzero and lower than the last available one before the visit and daily dose is nonzero at the visit. For example, in the sequence 14 mg/kg/day - 0 mg/kg/day - 7 mg/kg/day, the 7mg/kg/day dose will be counted as a reduction and in the sequence 14mg/kg/day - 7 mg/kg/day - 3.5 mg/kg/day, 3.5 mg/kg/day will be counted as two reductions.

The number and percentage of patients with dose interruption and/or dose reduction along with reasons for dose interruption/reduction will be summarized using the safety set. Dose increase will not be included in these summaries.

Listings of all doses of the study treatment along with dose reduction and dose interruption reasons will be produced using the Safety set.

2.7 Prior, concomitant and post therapies

Medications will be classified as prior or concomitant based on the following rules and will be coded using the WHO Drug Reference Listing (WHO DRL) dictionary that employs the WHO Anatomical Therapeutic Chemical (WHO ATC) classification system. Summaries will include:

- Prior medications will be defined to be drugs taken prior to the first dose of study medication.

- Concomitant medications will be medications taken during the on-treatment period. Medications which started prior to the first dose of study medication and continued thereafter will be counted in both summaries.

Concomitant medications and significant non-drug therapies prior to and after the start of study treatment will be listed and summarized according to the Anatomical Therapeutic Chemical (ATC) classification system using Safety set. Prior medication/therapies that started before the first dose of study treatment, or those starting after 30 days from the last day of study medication will be flagged in the listing.

2.7.1.1 Prior chelation therapy

History of iron chelation therapy is collected in prior or concomitant medication CRF page. By the drug name, the prior chelation therapy will be identified.

Prior chelation therapy will be summarized by lowest ATC class and preferred term. Summaries will include time from last treatment to start of study treatment. Duration of iron chelation prior to start of study treatment will be categorized into time intervals (< 1, 1-<3, 3- <6 and >=6 months of cumulative therapy). Duration of prior chelation therapy will be calculated based on start and the end date of the therapy, i.e. duration (days) = end date – start date+1. Frequency counts and percentages will be presented for the number of patients in each interval.

Prior chelation therapy and chelation naïve patients will be listed using FAS.

2.7.1.2 Blood transfusion history

The number of patients with prior blood transfusions within the period of 3 months prior to Screening visit 1, and the average amount of RBC (in mL/kg/day) will be summarized using descriptive statistics and listed using the FAS.

2.7.2 Post therapies

The study will end after last dose of study treatment plus 30 days follow-up. Post therapies, if any will be flagged in the listings.

2.8 Analysis of the primary objective

The primary objective of the study is to assess the safety of crushed deferasirox FCT with respect to selected gastrointestinal (GI) disorders.

2.8.1 Primary endpoint

The primary endpoint is the proportion of patients with selected gastrointestinal disorders (esophagitis, stomatitis, mouth ulceration, gastric ulcers, hemorrhage, abdominal pain, diarrhea,

nausea, and vomiting) up to 24 weeks including 30 days safety follow-up. Selected gastrointestinal disorders will be captured from AE page of eCRFs and PT term will be used. Corresponding PT terms will be oesophagitis, Barrett's esophagitis, stomatitis, mouth ulceration, gastric ulcer, gastrointestinal haemorrhage, abdominal pain, diarrhoea, nausea and vomiting. If patients discontinue earlier than 24-week visit, the patients will be followed 30 days after discontinuation of study treatment.

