2.1.1 General presentation of descriptive summaries

Qualitative data (e.g., gender, race, etc.) will be summarized by frequency count and percentages. Percentages will be calculated using the number of patients in the relevant population as the denominator.

Quantitative data (e.g., age, body weight, etc.) will be summarized by appropriate descriptive statistics (i.e. mean, standard deviation, median, minimum, and maximum). For selected parameters 25th and 75th percentiles will also be presented in box plots.

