2.2.2 Safety Analysis Set

The Safety Set includes all patients who received at least one dose of deferasirox FCT during the study. Note that the Safety Set and the FAS will be the same for this single arm phase IV study.

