2.8.2 Statistical hypothesis, model, and method of analysis

Proportion of patients with selected GI disorders will be provided together with the corresponding 95% confidence interval using the Clopper-Pearson exact method for this proportion (see [section 5.3.1](#)).

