2.8.3 Handling of missing values/censoring/discontinuations

Not applicable

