2.8.4 Supportive analyses

Exposure-adjusted adverse event incidence will be presented by the severity and preferred term for the **primary** analysis. It is defined as:

$$\frac{\text{Number of patients with new or worsened AEs on selected gastrointestinal disorder during on - treatment period}}{\text{Patient - Year exposure}/365.25}$$

Patient-year exposure is counted in days up to the first qualifying adverse event (or end of time at risk for subjects without adverse event), divided by 365.25.

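### The crude primary proportion counts event-free early leavers as non-events for the full 24 weeks plus 30 days, and no estimate of cumulative risk over that window is planned

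*SAP*

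**What the plan says.** SAP 2.8.1 states: "The primary endpoint is the proportion of patients with selected gastrointestinal disorders", over a window of up to 24 weeks including the 30-day safety follow-up. For early leavers it says: "If patients discontinue earlier than 24-week visit, the patients will be followed 30 days after discontinuation of study treatment". SAP 2.8.2 reports the proportion with a "95% confidence interval using the Clopper-Pearson exact method for this proportion".

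The denominator follows from two general rules. SAP 2.1.1: "Percentages will be calculated using the number of patients in the relevant population as the denominator". SAP 2.2.2: "The Safety Set includes all patients who received at least one dose of deferasirox FCT during the study". Protocol 7.1.5.1 says that leavers are not replaced.

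Under "Handling of missing values/censoring/discontinuations", SAP 2.8.3 has only "Not applicable". Protocol 10.4.3 has the same entry, and protocol 10.4.4 plans no sensitivity analysis.

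The SAP does plan one analysis that uses time at risk. In 2.8.4: "Exposure-adjusted adverse event incidence will be presented by the severity and preferred term". Time there runs to the first qualifying event or to the end of time at risk. SAP 2.5 will count children who discontinue before the week 24 visit, with the primary reason. SAP 2.6.2 will band the duration of exposure.

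**The concern.** The endpoint names a fixed window, but observation of a leaver ends 30 days after stopping. A child who stops at the end of week 3 is observed for 21 + 30 = 51 days, about 7 weeks, out of 168 + 30 = 198 days, about 28 weeks. If no selected event occurred by then, the child counts in the same way as one followed event-free to day 198.

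The study answers a regulator's request for safety data on these events, so a reader will probably take the headline percentage as the risk over the stated window. On that reading the unobserved time is credited as event-free. Any resulting error makes the product look safer, and it grows with dropout. A larger sample would not reduce it, and the Clopper-Pearson interval does not allow for it.

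**Working it through.** **The plan's own figure first.** SAP Table 3-1 gives, for 40 children, the chance of seeing at least one event, 1 − (1 − p)^40, and the Clopper-Pearson limits. All ten rows reproduce. For example, 3% gives 0.704 (printed 0.70) and 10% gives 0.985 (printed 0.99) with limits 0.028 to 0.237 (printed 0.03, 0.24). The table has no dropout term; it treats all 40 as fully observed.

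**Inputs.**
- Window: 24 × 7 + 30 = 198 days (SAP 2.8.1).
- Follow-up after stopping: 30 days (SAP 2.8.1).
- Dropout share d: not in the documents; assumed 5% to 30%, unrelated to GI risk, with stopping day T uniform over 168 days.
- True 198-day risk R: assumed 15%, 26% and 40%. The last two echo figures in protocol 1.2.1.2 and 1.2, but those describe other populations, formulations or follow-up lengths, so here they are only illustrations.
- Onset: constant hazard, F(t) = 1 − (1 − R)^(t/198); or front-loaded, with (t/198) replaced by its square root (Weibull, shape 0.5).

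**Formula.** Expected crude proportion = (1 − d)·R + d·mean F(T + 30). The shortfall is d·[R − mean F(T + 30)].

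**Worked case.** R = 40%, constant hazard: mean F(T + 30) = 24.9%. With d = 20%, 0.80 × 40% + 0.20 × 24.9% = 37.0%, a shortfall of 3.0 points.

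Expected crude proportion (shortfall in points), constant hazard, 30-day contact completed:

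| R | d = 5% | d = 10% | d = 20% | d = 30% |
|---|---|---|---|---|
| 15% | 14.7% (0.3) | 14.4% (0.6) | 13.8% (1.2) | 13.2% (1.8) |
| 26% | 25.5% (0.5) | 25.0% (1.0) | 23.9% (2.1) | 22.9% (3.1) |
| 40% | 39.2% (0.8) | 38.5% (1.5) | 37.0% (3.0) | 35.5% (4.5) |

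**Front-loaded onset.** The shortfall is about 40% smaller. R = 40% with d = 20% gives 38.2%, and the whole grid runs from 0.2 to 2.6 points.

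**If the 30-day contact is also lost.** R = 40%, constant hazard: mean F(T) = 18.9%, so d = 20% gives 0.32 + 0.20 × 0.189 = 35.8%. In the extreme case where all of that 20% are lost at day 14, F(14) = 3.5% and the crude proportion is 0.32 + 0.20 × 0.035 = 32.7%.

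**Scale.** The 95% Clopper-Pearson interval at 16/40 is 24.9% to 56.7%, a width of 31.8 points.

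**The case against.** A reader might infer that the primary result is simply biased low and that nothing in the plan deals with unequal follow-up. The documents do not support that, for four reasons.

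- **The target is not stated.** SAP 2.1.2.7 defines the on-treatment period as first dose to 30 days after last dose, and adverse event tables count treatment-emergent events. If the target is the incidence observed in that period, a child who stops early and completes the 30 days is fully observed, and having no censoring rule is coherent. The shortfall exists only against the risk over the full fixed window. This stands, although the endpoint does name such a window and the plan never says which target it means.
- **Part of it is already covered.** SAP 2.8.4, 2.5 and 2.6.2 address unequal follow-up. But 2.8.4 is a rate by severity and preferred term, with no interval, no cumulative risk and no explicit rate for the composite. Its numerator could be read as the composite, but the text does not settle this. A rate converts to a 198-day risk only under a constant hazard. The disposition and exposure tables are not split by event status.
- **Leaving because of a GI event is not the mechanism.** A child who stops because of a recorded selected GI event already counts as an event. The calculation above also draws dropout independently of GI risk, so it does not show what dropout from poor tolerability would do.
- **Lost contact should be uncommon.** Protocol 4.1 requires contact during the 30 days even with families who refuse a final visit. The main exception is withdrawal of consent (protocol 7.1.6), after which SAP 2.1 excludes newly collected data.

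It is also fair to say that no hypothesis is tested and no threshold depends on the estimate, so the shortfall cannot reverse a decision rule.

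**Conclusion.** The point holds in conditional form. The crude proportion treats an event-free early leaver as a non-event for the stated window. It understates the full-window risk if that risk is the target and if leaving is unrelated or positively related to GI risk. Under the assumed inputs the shortfall is about 0.3 to 4.5 percentage points with constant hazard and completed 30-day contact. It is smaller if events are front-loaded, and larger only if many children leave very early or miss the 30-day contact. The actual size cannot be fixed because no dropout rate is given.

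Against an interval about 32 points wide this is modest, and the primary analysis need not change. What is missing is an estimate with an interval that answers the fixed-window question for the composite, and a statement of how incomplete follow-up is treated.

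**What to change.** Keep the crude proportion with its Clopper-Pearson interval as the primary analysis. Then:

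- **SAP 2.8.4:** add a Kaplan-Meier cumulative incidence of the first selected GI event (composite) at day 168 and day 198, with 95% confidence intervals. Censor at the end of the on-treatment period (last dose plus 30 days) or at earlier loss of contact.
- **Assumption:** state that censoring is taken as non-informative, and that the estimate may still be low if children leave because of poor tolerability that was never recorded as an event.
- **Numbers at risk:** show them at both days. The week 24 visit has a ±7-day window (protocol Table 7-1), so a completer whose last dose falls on day 168 − 7 = 161 is censored at day 161 + 30 = 191, before day 198.
- **SAP 2.8.3:** replace the empty entry with one sentence saying that early leavers without an event count as non-events in the crude proportion, and pointing to the supportive analysis.
- **Disclosure:** report the number of event-free children observed for less than 24 weeks.

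While 2.8.4 is open, its denominator should be clarified. As printed, it can be read as dividing by 365.25 a quantity already defined as days divided by 365.25.

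The cost is one more supportive analysis from onset and dosing dates already collected, and a supportive incidence that may be slightly higher than the crude one.

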2.8.2 Statistical hypothesis, model, and method of analysis

Proportion of patients with selected GI disorders will be provided together with the corresponding 95% confidence interval using the Clopper-Pearson exact method for this proportion (see [section 5.3.1](#)).

2.8.2.1 Statistical hypothesis test

No hypothesis will be tested for this primary endpoint.

2.8.3 Handling of missing values/censoring/discontinuations

Not applicable

2.8.4 Supportive analyses

Exposure-adjusted adverse event incidence will be presented by the severity and preferred term for the **primary** analysis. It is defined as:

$$\frac{\text{Number of patients with new or worsened AEs on selected gastrointestinal disorder during on - treatment period}}{\text{Patient - Year exposure}/365.25}$$

Patient-year exposure is counted in days up to the first qualifying adverse event (or end of time at risk for subjects without adverse event), divided by 365.25.

2.9 Analysis of the key secondary objective

Not applicable

2.10 Analysis of secondary efficacy objective(s)

The secondary efficacy objective for this study is to assess the efficacy of deferasirox FCT treatment.

2.10.1 Secondary endpoints

The secondary efficacy endpoint for this study will be the change from baseline over time in serum ferritin (SF) up-to 24 weeks of treatment.

2.10.2 Statistical hypothesis, model, and method of analysis

A summary table will be provided for the change in SF from baseline for each visit up-to 24 weeks of treatment using FAS. A listing will also be provided including current SF level, change from baseline by visit and by patient. A graphical representation of SF change from baseline by box-plot will be provided for each visit using FAS.

For the summary table, all scheduled and unscheduled visits will be considered. If a scheduled visit does not occur, then an unscheduled visit will be mapped to a scheduled visit by the below rule:

- The target date of a scheduled visit will be defined relative to Day 1 as $(X-1)*7+1$, where X is the number of weeks, such as X=1, 2, ... For example, the target day for Week 12 visit will be $(12-1)*7+1 = 78$ days.
- Unscheduled visit then will be mapped to a scheduled visit by:
 - Weeks 2 and 3: -1 day / +1 day
 - Week 4 : -1 day/+7 days
 - Week 8,12,16, 20 and 24 (EOT): -7 days / +7 days

If a scheduled visit already exists, then no unscheduled visit will be mapped against a scheduled visit. If no scheduled visits exist, the unscheduled visit which is the closest to the target scheduled visit will be considered. If two unscheduled visits are equidistant from the targeted scheduled visit then prior to the targeted scheduled visit will be consider as scheduled visit. After mapping unscheduled visit to a scheduled visit, only scheduled visit will be considered for the summary level outputs.

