Urinary total protein/creatinine ratio	>1.0 mg/mg at two consecutive measurements at least 7 days apart
Total bilirubin	$>2 \times ULN$
Direct bilirubin	$>2 \times ULN$

Summaries for the change from baseline will be provided for all parameters. Creatinine clearance will be estimated using the (modified) Schwartz formula (additional details in [section 5.2](#)). An unscheduled visit will be mapped to a scheduled visit per [section 2.10.2](#).

Potential Hy's Law events are defined as patients with concurrent occurrence of AST or ALT $> 3 \times ULN$ and TBIL $> 2 \times ULN$ and ALP $< 2 \times ULN$ in the same assessment sample during the on-treatment period. Potential Hy's law events will be tabulated using Safety set.

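### SAP 2.10.2 maps unscheduled results by visit rather than by test, and with narrower windows than the protocol at Weeks 2, 3 and early Week 4

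*SAP*

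**What the plan says.** SAP 2.10.2 sets the rule for using unscheduled results in the ferritin summaries. Its trigger is the absence of the visit: "If a scheduled visit does not occur, then an unscheduled visit will be mapped to a scheduled visit by the below rule". The converse is also stated: "If a scheduled visit already exists, then no unscheduled visit will be mapped against a scheduled visit". Target days count from Day 1; for example, "the target day for Week 12 visit will be $(12-1)*7+1 = 78$ days". The permitted distances from target are "Weeks 2 and 3: -1 day / +1 day", "Week 4 : -1 day/+7 days" and "Week 8,12,16, 20 and 24 (EOT): -7 days / +7 days". After mapping, "only scheduled visit will be considered for the summary level outputs".

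The rule reaches beyond ferritin. SAP 2.11 applies it to the renal and hepatic box plots and shift tables. SAP 2.11.4 repeats it for laboratory data ("An unscheduled visit will be mapped to a scheduled visit per" section 2.10.2), and SAP 2.11.5.2 does so for vital signs. SAP 2.10.3 leaves a ferritin change as missing when either value is missing, and the imputation rules in SAP 5.1 cover dates only.

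Protocol Table 7-1 allows ±3 days at Weeks 2, 3 and 4, and ±7 days at Weeks 8, 12, 16, 20 and 24. Protocol 7.2.2.5.2 sets the tests due: creatinine and creatinine clearance at Week 2; these plus liver tests at Week 3; and the full panel with ferritin from Week 4 onwards.

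**The concern.** A mapping rule should recover a measured value when the planned one is absent. This rule can fail to do so in two ways.

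The trigger looks at attendance. A child who attends but whose sample is haemolysed or lost has a scheduled visit on record, so a redraw a few days later has no route into the by-visit summary. A child who missed the visit altogether would have the same redraw counted.

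The early windows are also tighter for a substitute than the protocol is for the visit itself, and the SAP gives no reason. Weeks 2 to 4 are the period of weekly renal and two-weekly hepatic monitoring. With a planned minimum of 40 children, each lost value is 1/40 = 2.5% of a full visit summary.

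**Working it through.** **Inputs.** Target-day rule and mapping windows: SAP 2.10.2. Visit windows: protocol Table 7-1. Tests due at each visit: protocol 7.2.2.5.2. The protocol does not number the nominal day of each visit after Day 1, so its windows are centred here on the SAP's own targets.

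**Target days.** Target = (X - 1) × 7 + 1. Week 12 gives 11 × 7 + 1 = 78, which reproduces the SAP's example. The other visits fall on Days 8, 15, 22, 50, 106, 134 and 162.

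**Windows compared day by day.**

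| Visit | Target | Protocol window | SAP mapping window | Protocol days not mapped | Extra SAP days |
|---|---|---|---|---|---|
| Week 2 | 8 | 5-11 (7 days) | 7-9 (3 days) | 5, 6, 10, 11 | none |
| Week 3 | 15 | 12-18 (7) | 14-16 (3) | 12, 13, 17, 18 | none |
| Week 4 | 22 | 19-25 (7) | 21-29 (9) | 19, 20 | 26-29 |
| Week 8 | 50 | 43-57 (15) | 43-57 (15) | none | none |
| Weeks 12, 16, 20, 24 | 78, 106, 134, 162 | target ±7 (15 each) | target ±7 (15 each) | none | none |

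The protocol windows at Weeks 2 to 4 run 5-11, 12-18 and 19-25. They adjoin without overlapping, so avoiding overlap cannot be the reason for the tighter rule. Days not mapped: 4 + 4 + 2 = 10 of 21.

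**By test**, counting only visits where the test is due:
- Creatinine (8 visits): 3 × 7 + 5 × 15 = 96 protocol-window days, 10 not mapped.
- Liver tests (7 visits, none at Week 2): 2 × 7 + 5 × 15 = 89 days, 4 + 2 = 6 not mapped.
- Ferritin (6 visits, from Week 4): 7 + 5 × 15 = 82 days, 2 not mapped (Days 19 and 20).

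In each case the SAP also adds four days (26-29) at Week 4.

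**Example of the window mismatch.** A scheduled Week 2 visit on Day 11, three days late, is used, because the mapping windows apply only to unscheduled visits. If the Week 2 visit is missed and creatinine is drawn at an unscheduled visit on Day 10, two days from target, it is not used.

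**Example of the visit-level trigger.** Child A misses Week 12 and has an unscheduled ferritin on Day 81. Days 71-85 are in the window, so it maps to Week 12. Child B attends on Day 78, the ferritin sample is lost, and it is redrawn on Day 81. The visit exists, so nothing is mapped and Child B's Week 12 change is missing. The same can happen with any test at any post-baseline visit.

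**The case against.** The strongest reply is that little is lost. The windows matter only when the scheduled visit was missed and an unscheduled one took place. Five of the eight windows equal the protocol's, and Week 4 is wider overall (9 days against 7). Unmapped results stay in the listing of all laboratory data and in the notable-value counts, which SAP 2.11.4 bases on scheduled and unscheduled visits. Potential Hy's Law events are defined over the on-treatment period, not by visit. The primary endpoint comes from the adverse event page. All of this stands and limits the point to secondary by-visit output.

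A programmer working test by test might also treat a missing ferritin record as a visit that did not occur. That would be sensible, but the SAP does not say it, and its literal wording says otherwise.

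Unscheduled tests are done when clinically indicated (protocol 7.1.9), so admitting more of them could tilt by-visit means. This is a real cost, but the SAP already accepts such values at every visit and does not give this as its reason for the early windows.

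Three stronger readings are tempting, and the documents do not support them:
- *Nearly half of all study days are dropped.* Over Days 2-169, 3 + 3 + 9 + 5 × 15 = 90 of 168 days map, leaving 78 (46%). But 78 - 10 = 68 of those (87%) also lie outside every protocol window, and days are not results.
- *The ±1-day window harms the ferritin endpoint.* Ferritin is not due at Weeks 2 or 3. Through the windows it loses two days and gains four; its main exposure is the visit-level trigger.
- *Confidence intervals for mean change will widen.* None is planned for ferritin or laboratory change, only descriptive statistics and plots.

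**Conclusion.** Both defects are confirmed, and both are minor. The visit-level trigger matters more: read literally, it blocks an in-window redraw of any test at every mapped visit, including ferritin at Weeks 4 to 24. The window mismatch is confined to Weeks 2 and 3 and the early side of Week 4, where 10 of 21 protocol-window days (5, 6, 10-13, 17-20) map to nothing. It affects creatinine at Weeks 2 to 4, liver tests at Week 3 and early Week 4, and ferritin on Days 19 and 20 only. Vital signs, due at all these visits, are exposed in the same way as creatinine.

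The effect is limited to secondary by-visit summaries, box plots and shift tables. The SAP leaves one boundary unclear: section 2.11.4 promises shift tables to the worst on-treatment value, while section 2.11 ties shift tables to scheduled visits after mapping.

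The day counts assume that the protocol's windows are centred on the SAP's targets. The number of results lost cannot be estimated, because the documents give no rate of missed visits, lost samples or unscheduled tests.

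**What to change.** Amend the mapping paragraph in SAP 2.10.2 in two places.

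1. Apply the rule per parameter, for example: *if no non-missing result for a parameter exists at the scheduled visit, use the closest unscheduled result for that parameter within the window.* The existing tie rule can stay.
2. Set the mapping windows to ±3 days at Weeks 2 and 3 and -3/+7 days at Week 4, and leave Weeks 8 to 24 at ±7. The windows become Days 5-11, 12-18 and 19-29, with Week 8 opening on Day 43. None overlap, and all 10 days are recovered.

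The cross-references in SAP 2.11, 2.11.4 and 2.11.5.2 then carry the change through. One added sentence could say whether the worst-on-treatment shift tables use all results or only mapped ones.

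The cost is a paragraph of text and a small programming change, with no new data. A few more clinically triggered values would enter the by-visit summaries. Closing the remaining gaps with windows wider than ±7 days is not recommended here: it would depart from the protocol's own windows, and leaving Week 24 open to the end of the on-treatment period (30 days after last dose) could count off-drug values as Week 24.
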